# 7.4 **S**CREENING

Subjects will be recruited for the study through the clinical practices of the Investigators.

#### CONFIDENTIAL AND PROPRIETARY

This document contains information that is confidential and proprietary to Smith + Nephew PLC and Smith + Nephew, Inc. and is intended for use only by Smith + Nephew and its manufacturer. It shall not be reproduced or copied in whole or in part, nor shall the contents be disclosed by any means without prior written permission from Smith + Nephew, nor shall anyone make any use of it that is contrary to the expressed or implied wishes of Smith + Nephew.

Study Protocol	Smith&nephew	
A prospective, multi-center, single arm PMCF study to evaluate the safety and performance of ENTACT™ (Next Generation) resorbable septal staple system for septoplasty	Number: ENTACT.ENT.PRO.SEP.2019.05	
	Version: 2.0, 27Aug2020	
	Page: Page 38 of 94	

40 individuals to be approached for participation. Subjects will be enrolled as they meet eligibility and consent to the study.

Participating study sites are required to document all screened subjects considered for inclusion in this study. If a subject is excluded from the study, the reasons for exclusion will be documented in the subject's source documents and noted on the Screening and Enrollment Log. All screening activities that occur prior to consent shall be referred to as pre-screening.

Any subject that meets the definition of a Vulnerable Subject [per International Organization for Standardization (ISO) 14155:2011 Section 3.44.] should be reviewed, but not excluded from the study.

### 7.5 INFORMED CONSENT

Before conducting any study procedures or examinations, informed consent shall be obtained from all participants according to ISO14155 guidelines, the Health Insurance Portability and Accountability Act (HIPAA, if applicable), and local regulations. Patients must be informed as to the purpose of the study and the potential risks and benefits known or that can be reasonably predicted or expected as described in the written Informed Consent Form (ICF). The patients shall have sufficient opportunity to consider participation in the study. Patients will then be invited to read, sign and personally date the Institutional Review Board (IRB)-approved ICF, indicating their consent for enrollment. Additionally, the individual who obtains consent from the participant will sign and date the ICF. A copy of the signed informed consent documentation will be provided to the participant, and the original filed in the investigator site file (ISF).

In the case of vulnerable subjects, the ICF must be understood and signed by the subject's legally authorized representative (parent or legal guardian). Assent to participate in the study should be obtained for subjects ≥7 years of age and <18 years of age if allowed by local regulations. For subjects less than 7 years of age an assent will not be obtained.

This document contains information that is confidential and proprietary to Smith + Nephew PLC and Smith + Nephew, Inc. and is intended for use only by Smith + Nephew and its manufacturer. It shall not be reproduced or copied in whole or in part, nor shall the contents be disclosed by any means without prior written permission from Smith + Nephew, nor shall anyone make any use of it that is contrary to the expressed or implied wishes of Smith + Nephew.

Study Protocol	% smith&nephew	
A prospective, multi-center, single arm PMCF study to evaluate the safety and performance of ENTACT™ (Next Generation) resorbable septal staple system for septoplasty	Number: ENTACT.ENT.PRO.SEP.2019.05	
	Version: 2.0, 27Aug2020	
	Page: Page 39 of 94	

In the case of minors, the ICF must be obtained by their legally designated representative. The minor shall participate in the informed consent process in a way suitable for his/her age and mental maturity. Minors will receive the study information in a way adapted to their age and mental maturity from investigators or members of the investigating team who are trained or experienced in working with children. If minors express a wish or an opinion with regards to study participation this needs to be respected by the Investigator. If during the study, the minor reaches the age of 18 years (legal competence), the informed consent shall be obtained again, before the subject can continue to participate in the clinical investigation.

Study research staff may then complete Visit 1 Initial Visit (Screening/ Pre-Operative) with the subject. If a subject refuses participation, no further information will be collected. Reason for exclusion should be noted on the Screening and Enrollment Log.

### 7.6 ENROLLMENT

Subjects for whom the consent process has been completed and have been treated with the study product are considered enrolled.

Subjects will be assigned a Subject ID at the time of consent.

### 7.7 SCREEN FAILURES

Subjects who have provided consent, completed screening, and for any reason do not meet the eligibility criteria, were not enrolled by the Investigator for any reason, or withdraw consent for any reason prior to enrollment, will be considered a consented screen failure. For these subjects, record the reason for screen failure on the Screening and Enrollment Log and complete the End of Study Case Report Form (CRF) documenting the primary reason for discontinuation. Consented screen failures will be replaced without limit by newly enrolled subjects.

This document contains information that is confidential and proprietary to Smith + Nephew PLC and Smith + Nephew, Inc. and is intended for use only by Smith + Nephew and its manufacturer. It shall not be reproduced or copied in whole or in part, nor shall the contents be disclosed by any means without prior written permission from Smith + Nephew, nor shall anyone make any use of it that is contrary to the expressed or implied wishes of Smith + Nephew.

Study Protocol	Smith&nephew
A prospective, multi-center, single arm PMCF study to evaluate	Number:
the safety and performance of ENTACT™ (Next Generation) resorbable septal staple system for septoplasty	ENTACT.ENT.PRO.SEP.2019.05
	Version: 2.0, 27Aug2020
	Page: Page 40 of 94

# 7.8 LOST TO FOLLOW-UP

A subject will be considered lost to follow-up if he/she does not appear for the scheduled study visit for two consecutive visits and does not return for a final visit, and study personnel are unable to contact the subject.

Some actively enrolled subjects will not return for follow-up exams on time. Study personnel must make a reasonable effort to contact the subject and document the following contact attempts before declaring a subject to be lost to follow-up (LTFU): the subject has been contacted according to the site's policies, but no fewer than two documented phone contacts and one certified letter without response. Copies of all attempts to reach the subjects by mail or email and/or the attempts to contact the subject via other means should be documented, and that documentation should be kept with the subject's source documents at site.

# 7.9 WITHDRAWAL

All reasonable efforts should be made to collect 42 day postoperative data on all subjects enrolled in this study.

# 7.9.1 Withdrawal from Treatment

The Investigator may withdraw subjects from the study for many reasons, including but not limited to, the following:

- subject noncompliance (e.g., did not follow instructions);
- subject lost to follow-up;
- if the Investigator or the Sponsor stops the study for any reason and decides to withdraw subject(s) from the study;
- Adverse Events/Adverse Device Effects that affect the ability to evaluate the study product without bias;

This document contains information that is confidential and proprietary to Smith + Nephew PLC and Smith + Nephew, Inc. and is intended for use only by Smith + Nephew and its manufacturer. It shall not be reproduced or copied in whole or in part, nor shall the contents be disclosed by any means without prior written permission from Smith + Nephew, nor shall anyone make any use of it that is contrary to the expressed or implied wishes of Smith + Nephew.

Study Protocol	Smith&nephew
A prospective, multi-center, single arm PMCF study to evaluate the safety and performance of ENTACT™ (Next Generation) resorbable septal staple system for septoplasty	Number: ENTACT.ENT.PRO.SEP.2019.05
	Version: 2.0, 27Aug2020
	Page: Page 41 of 94

- any other significant reason identified by the Investigator;
- re-intervention.

For each case, information will be obtained in the source document and the Case Report Form (CRF), detailing circumstances leading to the withdrawal.

Subjects who drop out or are withdrawn will not be re-entered into the study at a later date.

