#### 8.4.3 Investigator Training

Prior to the clinical trial, the clinical research associate (CRA), coordinating with the persons in charge of the study sites, will train the Investigators on the study protocol, making sure they are familiar with the use of investigational medical device, and implement subject enrollment strictly in accordance with the inclusion criteria and exclusion criteria, conduct relevant examinations according to the protocol requirements, also master all new device-related information found during the clinical trial, thus to minimize the interferential factors. The follow-up exams will be delegated to Investigators not involved in the procedure to reduce potential bias by the surgeon.

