### 9.1.7 Discontinued Subjects

Discontinued subjects are those who voluntarily discontinue participation, who are withdrawn for reasons of safety, who are lost to follow-up, or who have missed 2 study visits. Where possible, a full End of Study Visit should be completed for all subjects who discontinue the study early. Where consent is withdrawn, the date and any reason given for discontinuation should be captured, at a minimum (**see Section 7.9**).

Finally, if appropriate, the Investigator will also advise the subject of subsequent therapy and/or procedures necessary for their medical condition. Medical care will not be provided to the

This document contains information that is confidential and proprietary to Smith + Nephew PLC and Smith + Nephew, Inc. and is intended for use only by Smith + Nephew and its manufacturer. It shall not be reproduced or copied in whole or in part, nor shall the contents be disclosed by any means without prior written permission from Smith + Nephew, nor shall anyone make any use of it that is contrary to the expressed or implied wishes of Smith + Nephew.

Study Protocol	>∕smith&nephew
A prospective, multi-center, single arm PMCF study to evaluate the safety and performance of ENTACT™ (Next Generation) resorbable septal staple system for septoplasty	Number: ENTACT.ENT.PRO.SEP.2019.05
	Version: 2.0, 27Aug2020 Page: Page 52 of 94

subject after the clinical investigation is completed, other than the standard care provided by the site, which is not considered a study visit(s).

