### 10.4 EFFICACY ANALYSIS

## **10.4.1 Analysis of Primary Endpoint**

Data will be collected on whether the septum wall appearance and need for re-intervention at the surgery site are due to the device or the procedure. Only those that are device-related will contribute to the primary endpoint analyses, in line with the primary objective of this study. A binary variable will be defined as follows; one if all five of the following criteria are true and 0 if at least one of the criteria is false:

- Septum wall straight appearance
- Complete coaptation of perichondrial flaps on septum wall
- Absence of significant local tissue reaction at the staple site
- Absence of hematoma swelling at the staple site
- No need for re-intervention at the surgery site

Clinical success will be inferred for a patient if their binary variable is 1. Clinical success will be reported as a count and percentage with a 95% CI using Clopper-Pearson Exact methodology. A logistic model will be used to evaluate the adjusted and unadjusted models for the primary outcome variable. The variables considered important and to be included in the final model are age and BMI. All other baseline and medical factors collected at baseline will be evaluated for

This document contains information that is confidential and proprietary to Smith + Nephew PLC and Smith + Nephew, Inc. and is intended for use only by Smith + Nephew and its manufacturer. It shall not be reproduced or copied in whole or in part, nor shall the contents be disclosed by any means without prior written permission from Smith + Nephew, nor shall anyone make any use of it that is contrary to the expressed or implied wishes of Smith + Nephew.

Study Protocol	Smith&nephew
A prospective, multi-center, single arm PMCF study to evaluate the safety and performance of ENTACT ™ (Next Generation) resorbable septal staple system for septoplasty	Number: ENTACT.ENT.PRO.SEP.2019.05
	Version: 2.0, 27Aug2020
	Page: Page 56 of 94

importance in adjusted models and only those statistically significant in an unadjusted model will be considered in the final model.

This analysis will be carried out using the FAS as the primary analysis population and the PP population using for sensitivity analysis.

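### Section 7.9.1 lets the investigator end a subject's follow-up for an adverse event, so the Day-21 primary endpoint can be missing in a way that depends on outcome, and 10.4.1 has no rule for scoring it

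*Combined protocol and SAP*

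**What the plan says.** Section 7.9 opens with the follow-up aim: "All reasonable efforts should be made to collect 42 day postoperative data on all subjects enrolled in this study". Section 7.9.1 is headed Withdrawal from Treatment, but its text is about leaving the study: "The Investigator may withdraw subjects from the study for many reasons, including but not limited to, the following". One listed reason is "Adverse Events/Adverse Device Effects that affect the ability to evaluate the study product without bias"; another is "any other significant reason identified by the Investigator". The section sets no time limit and no independent review, and a withdrawn subject cannot re-enter later.

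Section 9.1.7 counts among discontinued subjects those "who are withdrawn for reasons of safety, who are lost to follow-up, or who have missed 2 study visits". It asks for an End of Study visit where possible. Section 7.9.3 deals only with data after withdrawal of consent and says nothing about withdrawal by the investigator.

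The primary endpoint (8.3.1, 10.4.1) is a Day-21 composite, scored "one if all five of the following criteria are true and 0 if at least one of the criteria is false". Two of the five criteria are the absence of significant tissue reaction and the absence of hematoma at the staple site. Section 10.2 admits to the FAS anyone recruited who has at least one post-baseline visit. Section 8.2.2 states that the study is not blinded. Section 8.4.3 adds one safeguard: "The follow-up exams will be delegated to Investigators not involved in the procedure to reduce potential bias by the surgeon".

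**The concern.** In a drug trial, stopping treatment and stopping follow-up are different acts. Here the staples are placed once on Day 0 and resorb, so there is no continuing treatment to withdraw. Whatever the heading says, 7.9.1 can only end observation.

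The AE/ADE ground then works against its stated purpose. A hematoma or significant tissue reaction at the staple site is an adverse event and also one of the outcomes the Day-21 exam is there to detect. Removing such a subject in order to protect an unbiased evaluation would introduce bias.

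The decision belongs to an investigator in an open, single-arm study, with no comparator in which similar losses might offset these. The uninvolved examiner required by 8.4.3 cannot help if the exam never takes place. What is at stake is the primary success rate.

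**Working it through.** **1. Path of one subject.** Take a subject with a staple-site hematoma who attends the Day 5±2 visit and is withdrawn on Day 8, before the Day 21±7 window opens on Day 14.

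- 10.2: in the FAS, because one post-baseline visit has been made.
- 10.4.1: scores 1 if all five criteria are true and 0 if any is false. With no Day-21 exam, neither value is defined.
- 9.1.7: an exit exam may exist, but nothing links it to the Day-21 endpoint.
- 7.9.3: does not apply, because consent was not withdrawn.

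The subject is in the primary population without a primary outcome, and the plan does not say what happens next.

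**2. The plan's own allowance for loss.** Section 11 needs 36 evaluable subjects and allows 10% drop-out: 36 / (1 − 0.10) = 40, which reproduces the enrolled number. At a true rate of 92%, the probability that a Wald 95% interval has half-width at most 0.11 is 84.3% at n = 36, which reproduces the stated minimum of 80%. (With the Clopper-Pearson interval planned in 10.4.1 it is 67.5%; that is a separate matter.) The inflation replaces up to four lost subjects in number. It treats their loss as unrelated to outcome and corrects nothing if it is related.

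**3. Size, under stated assumptions.** Of n = 40 treated, let k be withdrawn before Day 21 after a device effect and let m = 3 of the rest fail. I chose m = 3 because 8% of 38 is 3.04, in line with the 92% in Section 11. The number of successes is s = 40 − 3 − k. The rate is s/(40 − k) if the withdrawn subjects leave the denominator and s/40 if they count as failures. Intervals are Clopper-Pearson: lower limit = Beta quantile at 0.025 with (x, N − x + 1), upper limit = Beta quantile at 0.975 with (x + 1, N − x), where x is the number of successes and N the denominator used.

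| k | Left out | Counted as failures | Difference (points) |
|---|---|---|---|
| 1 | 36/39 = 92.3% (79.1 to 98.4) | 36/40 = 90.0% (76.3 to 97.2) | 2.3 |
| 2 | 35/38 = 92.1% (78.6 to 98.3) | 35/40 = 87.5% (73.2 to 95.8) | 4.6 |
| 3 | 34/37 = 91.9% (78.1 to 98.3) | 34/40 = 85.0% (70.2 to 94.3) | 6.9 |
| 4 | 33/36 = 91.7% (77.5 to 98.2) | 33/40 = 82.5% (67.2 to 92.7) | 9.2 |

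Four exits would use the whole drop-out allowance. In the left-out column the rate stays near 92% however many are removed.

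**4. Bounds for k = 2.** If both events would have resolved by Day 21, the best case is 37/40 = 92.5% (79.6 to 98.4). The worst case is 35/40 = 87.5%. The true result lies between them, and leaving the two out gives 92.1%, close to the favourable end.

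**5. How many events to expect.** Table 4.4.1-1 gives literature counts of 1/153 for hematoma and 5/153 for inflammation. Per 40 subjects that is 40 × 1/153 = 0.26 and 40 × 5/153 = 1.31, about 1.6 together. The table's maximum allowed counts are 2/40 and 4/40. Two exits is therefore an illustration within the protocol's own limits, not a forecast.

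**The case against.** The strongest reply is that the real gap is a missing-data rule. Section 10 says the SAP will be finalized before database lock; a rule there would settle the scoring whatever 7.9.1 says. The study estimates a rate, and 10.4.1 sets no performance goal, so no decision flips in these scenarios. This stands in part. A later rule can score a missing exam but cannot recover one that was never made, and 8.3.7 itself relies on pre-specification to limit reporting bias.

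Several stronger readings are tempting, and the documents do not support them:

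- *That 7.9.1 removes failures.* It is permissive. Its AE/ADE ground covers only events that impair unbiased evaluation, and one can argue that a hematoma is exactly what the exam evaluates. The open list and the catch-all reason make that a weak limit, but the rule allows such exits and does not require them.
- *That 7.9 and 7.9.1 flatly contradict each other.* Section 7.9 asks for reasonable efforts and 9.1.7 adds an exit visit where possible. The conflict is one of intent.
- *That AE outcomes are lost on exit.* Section 12.5.1 follows related ongoing events until they resolve or become chronic, and unrelated ones for up to 30 days; 12.5 recommends a follow-up visit.
- *That such exits are hidden.* Section 7.9.1 records the circumstances in the source document and CRF, and Section 18 requires an End of Study CRF with the reason. Only a tabulation is unstated.
- *That the operating surgeon decides.* The text says the Investigator, which neither names nor excludes the surgeon.
- *That any staple-site infection is a primary failure.* Infection is not one of the five criteria.
- *That 35/38 is the planned analysis.* No section says withdrawn subjects leave the denominator.

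The inflammation reported in the literature summary (4.2.2) was mild at one week, whereas the endpoint asks about significant reaction, so the event counts above may overstate qualifying cases.

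**Conclusion.** The concern holds in limited form. Section 7.9.1 permits follow-up to end because of events that are themselves primary-endpoint failures, after a one-time implant, at the discretion of an unblinded investigator, and no section scores the resulting missing Day-21 exam. The harm is to the primary success rate; safety follow-up and the recording of exit reasons are largely protected elsewhere.

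With two exits the reported rate could be 92.1% where counting them as failures gives 87.5%, a gap of 4.6 points; across one to four exits the gap runs from 2.3 to 9.2 points. These figures rest on three assumptions: the number of exits, three failures among the remaining subjects, and withdrawn subjects being dropped from the denominator. Counting every such exit as a failure is itself conservative, so the gap is an upper limit on the bias in each scenario.

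**What to change.** Reconcile 7.9, 7.9.1, 9.1.7 and 10.4.1 as follows.

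- **7.9.1 and 9.1.7:** an AE or ADE is not a ground for ending study follow-up. Treated subjects keep their scheduled visits to Day 42 unless they withdraw consent or are lost to follow-up. Correct the 7.9.1 heading to match its text. Whether noncompliance and the catch-all stay on the list is closer to preference; if the catch-all stays, state that it may not be used for an AE or ADE. The rule in 9.1 ending data collection at re-intervention is a separate matter.
- **10.4.1:** in the FAS analysis, count a subject who exits before the Day-21 exam after a device-related staple-site AE as a failure. Add a best/worst-case sensitivity analysis for all missing Day-21 exams.
- **Reporting:** tabulate every exit before Day 21 by reason, using the data already captured in the CRF.

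The cost is wording, since the visits are already scheduled. The reported success rate may be slightly lower, and an event that would have resolved by Day 21 is scored conservatively; the best-case analysis shows how much that matters.

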## 7.9.2 Subject's Withdrawal of Consent to Participate in Study

Study participation is voluntary, and subjects may withdraw at any point during the study without giving their reason for doing so. Where subjects withdraw consent, the Investigator should make a reasonable effort to ascertain the reason(s), while fully respecting the subject's privacy. The reason for withdrawal will be recorded in the CRF and source documents.

## 7.9.3 Use of Data Following Withdrawal

In cases where the subject withdraws consent, the data collected up to the point of withdrawal may be used, but no additional data for that subject may be collected.

# 8. STUDY DESIGN

# 8.1 STUDY DESIGN

This is a prospective, multi-center, single arm PMCF study to evaluate the safety and performance of the ENTACT (Next Generation) resorbable staple system for septoplasty in 40 subjects. The study purpose is to provide evidence to satisfy the PMCF requirements of CE Marking to market this device in Europe (data may be used to support registrations on other countries as well).

This study will enroll at up to 3 clinical sites in the United States.

This document contains information that is confidential and proprietary to Smith + Nephew PLC and Smith + Nephew, Inc. and is intended for use only by Smith + Nephew and its manufacturer. It shall not be reproduced or copied in whole or in part, nor shall the contents be disclosed by any means without prior written permission from Smith + Nephew, nor shall anyone make any use of it that is contrary to the expressed or implied wishes of Smith + Nephew.

Study Protocol	% smith&nephew	
A prospective, multi-center, single arm PMCF study to evaluate the safety and performance of ENTACT™ (Next Generation) resorbable septal staple system for septoplasty	Number: ENTACT.ENT.PRO.SEP.2019.05	
	Version: 2.0, 27Aug2020	
	Page: Page 42 of 94	

This is an open-label study with consecutive enrollment. The study will continue for 6 weeks from the date that the last subject received the study treatment to the date that the last subject completes the study as planned. Only subjects who meet the enrollment criteria as listed in **section 7** will be enrolled in the study. The study duration is an estimated 8 months from first study site initiation to last subject last visit.

Figure 8.1-1: Study Flowchart

